rPFS	Radiographic progression-free survival
SAE	Serious adverse event
SAP	Statistical Analysis Plan
SD	Stable disease
SOC	System Organ Class
TEAE	Treatment emergent adverse event

5. Study Objectives

Objectives	Endpoints
Primary	

 To characterize the efficacy of abemaciclib in combination with irinotecan + temozolomide 	
 PFS as determined by BIRC using RECIST 1.1
Secondary	

 To evaluate the safety profile of abemaciclib, irinotecan, and temozolomide combination 	
 Safety (including but not limited to): TEAEs, SAEs, deaths, laboratory abnormalities, vital signs, and physical examinations

 To characterize the clinical activity of abemaciclib, irinotecan, and temozolomide combination 	
 OS ORR DoR DCR PFS as determined by investigator assessment using RECIST 1.1

 To characterize the PK of abemaciclib in combination with irinotecan + temozolomide 	
 Concentrations of abemaciclib

 To assess the acceptability and palatability of the age-appropriate tablet and/or granule drug product, including dispersed tablets and/or granules 	
 Assessment of tablet, granule, or dispersed drug product presentation, including acceptability and palatability
Exploratory	

 To explore the relationship between abemaciclib concentrations and clinical outcomes 	
 Outcomes such as clinical efficacy and safety

 To explore correlation of biomarkers to clinical outcomes 	
 Outcomes such as clinical efficacy and/or exposure parameters

Abbreviations: BIRC = blinded independent review committee; DCR = disease control rate; DoR = duration of response; ORR = objective response rate; OS = overall survival; PFS = progression-free survival; PK = pharmacokinetics; RECIST 1.1 = Response Evaluation Criteria in Solid Tumors, Version 1.1 (Eisenhauer et al. 2009); SAEs = serious adverse events; TEAE = treatment-emergent adverse event.

6. Study Design

6.1. Study Design

6.1.1. Summary of Study Design

Study JP04, combined with Protocol J1S-MC-JAAA (hereinafter referred to as the CAMPFIRE Master Protocol), is a multicenter, randomized, open-label, Phase 2 study in participants with relapsed or refractory Ewing's sarcoma.

Participants will be randomized 2:1 to receive abemaciclib in combination with irinotecan and temozolomide versus irinotecan and temozolomide alone. Patients will be treated until disease progression or other discontinuation criteria are met.

The primary endpoint is PFS per RECIST 1.1 as determined by a blinded, independent review committee, and the primary analysis will utilize a Bayesian-augmented control arm to incorporate historical data. See Section 7.7.1 for full detail on the Bayesian model and historical data to be incorporated. Figure JP04.6.1 illustrates the study design.

[figure not shown]

Figure JP04.6.1. Illustration of study design.

Abbreviations: n = number of participants; PFS = progression-free survival.

^a One futility analysis will occur after approximately CCI events have been observed. See Section 7.12.2.

6.1.2. Determination of Sample Size

At least 45 participants will be enrolled in the study using a 2:1 randomization ratio. The primary objective of this study is to compare the efficacy of abemaciclib in combination with irinotecan and temozolomide (Arm A) to irinotecan and temozolomide (Arm B), in terms of PFS by blinded independent review committee, in participants with relapsed or refractory Ewing's sarcoma.

Participants who are randomized but not administered treatment may be replaced to ensure that enough participants may complete the study.

Under a frequentist analysis, the study will be powered to approximately CCI assuming a PFS HR of CCI at a 1-sided alpha of CCI. This requires approximately CCI events from all randomized

participants and accounts for the futility analysis described in Section 7.12.2. However, as described in Section 7.7.1, the primary analysis will incorporate a Bayesian Augmented Control and Bayesian decision rule, altering the exact operating characteristics above. Specifying the same one-sided Type I error rate of α the Bayesian Augmented Control may increase power as high as approximately α . Section 7.7.1.6 describes the results of a simulation study to evaluate the operating characteristics of the Bayesian decision rule under varying assumptions.

6.2. Method of Treatment Assignment

Before each participant's enrollment into the study, an eligibility check must be conducted by the investigational site. Upon confirmation of eligibility, the site will register the participant by assigning the participant a unique study identification number via the IWRS, which is accessible 24 hours a day. Study treatment will be allocated to participants using the IWRS. Participants who meet all enrollment criteria will be randomly assigned to receive study treatment.

Participants will be stratified by

- time to recurrence (<2 or ≥ 2 years from initial diagnosis) (Leavey et al. 2008),
- isolated pulmonary metastases vs other metastases (Leavey et al. 2008), and
- age (<18 years or ≥ 18 years).

7. A Priori Statistical Methods

7.1. General Considerations

Statistical analysis of this study will be the responsibility of Lilly or its designee. The interpretation of the study results will be the responsibility of the Lilly CRP/CRS and statistician. The CRP/CRS and statistician will also be responsible for the appropriate conduct of internal reviews for both the final study report and any study-related material to be authorized by Lilly for publication.

Any change to the data analysis methods described in the protocol will require an amendment ONLY if it changes a principal feature of the protocol. Any other change to the data analysis methods described in the protocol and the justification for making the change will be described in the clinical study report.

For Bayesian analyses, posterior medians and CCI (equal tailed) Bayesian credible intervals will be provided for relevant quantities unless otherwise stated below. Full detail regarding specification of prior distributions for prespecified Bayesian analyses are provided in Section 7.7.1.3.

All frequentist tests of treatment effect will be conducted at a 1-sided alpha level of CCI unless otherwise stated, and all CIs will have 2-sided coverage equal to CCI

7.1.1. Populations for Analysis

The following analysis sets will be defined for this study:

Intention-to-treat (ITT) analysis set: will include all randomized participants. The ITT analysis of efficacy data will consider allocation of participants to treatment groups as randomized and not by actual treatment received. This analysis set will be used for all baseline and efficacy analyses.

Safety analysis set: will include all randomized participants who received any quantity of study treatment, regardless of their eligibility for the study. The safety evaluation will be performed based on the first doses of study treatment a participant actually received, regardless of the arm to which he or she was randomized. The safety analysis set will be used for all dosing/exposure, safety, and resource utilization analyses.

Pharmacokinetic analysis set: will include all participants who received at least 1 dose of any study drug, have at least 1 evaluable PK sample, and sufficient dosing information.

Biomarker analysis set: will include the subset of participants from the ITT population from whom a valid assay result has been obtained.

7.1.2. Handling of Dropouts and Missing Data

Baseline will refer to the last nonmissing observation before first administration of any treatment unless stated otherwise. Missing data, except for dates, will not be imputed. When dates are used in calculations, missing days will be replaced with 15th of the month and missing day/month

with 01 JULY. Where windows are allowed for data collection and there is more than 1 reading in any window, appropriate consideration will be given as to whether only 1 value from the window should be used, and if so how it should be chosen. This could either be the mean (geometric mean) or the value closest to the mid-point of the window or the value closest to the data collection time of another variable if the analysis involves time-matched analyses.

Detailed censoring rules for evaluation of the primary PFS endpoint are provided in [Table JP04.7.1](#).

7.1.3. Multiple Comparisons/Multiplicity

No adjustments for multiplicity are planned for any secondary or exploratory endpoints.

7.2. Patient Disposition

A detailed description of patient disposition will be provided. It will include a summary of the number and percentage of screened patients randomized in the study, reasons for discontinuation from study treatment, and reasons for discontinuation from the study. Reason for discontinuation from both study treatment and the study will be listed by the predetermined categories. For treatment discontinuation, these include progressive disease, AE, death, withdrawal by subject, physician decision, noncompliance with study drug, protocol deviation, study terminated by the IRB/ERB/sponsor, lost to follow-up; for study discontinuation, these include study terminated by sponsor, withdrawal by subject, lost to follow-up, death. If the reason for discontinuation is AE or death, the associated AE or cause of death will be reported. The disposition will also be listed. All patients randomized in the study will be included in the summaries and listings.

7.3. Patient Characteristics

Patient characteristics will be summarized and listed for all patients randomized by treatment, including:

- Patient demographics (including age, sex, race and ethnicity, screening height and weight, and screening derived body surface area)
- Baseline disease characteristics (including disease staging, metastatic site(s), performance status at baseline, time-to-relapse after front-line therapy for advanced disease, number of prior lines of systemic therapy for advanced disease, prior radiotherapy, prior surgery and associated outcome)

7.4. Treatment Compliance

Treatment compliance for oral drugs will be derived from the difference between the total number of capsules/tablets dispensed and returned over the course of the patient's treatment, or the difference in weights of oral granule bottles. The number of cycles received, dose omissions, dose reductions, dose delays, and dose intensity will be summarized for all treated patients by cohort. Compliance will be assessed as the proportion of treatment that is actually taken, relative to what is expected, after accounting for protocol-defined dose adjustments. The proportion of patients who are  compliant with abemaciclib will be reported.

Intravenous (IV) study drugs will be administered only at the investigational sites by the authorized study site personnel. As a result, treatment compliance is ensured for any IV drugs.

7.5. Product Acceptability and Palatability

Responses from the drug product acceptability and palatability questionnaires for tablets and oral granules taken swallowed whole, dispersed in food or liquid, or dispersed and administered through a nasogastric or gastrostomy tube will be summarized categorically (frequency and percentage) by age group, for each visit separately and in aggregate. In addition, general trends in acceptability and palatability from Cycle 1 Day 1 (baseline), Cycle 2 Day 1, and Cycle 3 Day 1 will be analyzed.

7.6. Concomitant and Post-Discontinuation Therapy

Prior and concomitant medications and therapies (e.g., transfusions) will be listed and summarized by treatment arm for the safety population in each study.

The numbers and percentages of patients receiving postdiscontinuation anticancer therapies will be provided by type of therapy (surgery, radiotherapy, or systemic therapy), and by drug class and/or name, overall and by line of therapy.

7.7. Efficacy Analyses

7.7.1. Primary Outcome and Methodology

7.7.1.1. Definition

The primary endpoint of this study is progression-free survival by blinded, independent, review committee (PFS by BIRC). PFS is defined as the time from randomization until the first occurrence of documented disease progression per RECIST 1.1 criteria, or death from any cause in the absence of progressive disease, whichever comes first. A secondary endpoint will also consider documented disease progression as determined by investigator assessment, as described in Section 7.7.1.7. Participants known to be alive and without disease progression will be censored at the time of the last adequate tumor assessment (a detailed PFS event/censoring scheme is provided in Table JP04.7.1).

Table JP04.7.1. PFS Event/Censoring Scheme

Situation	Event/Censor	Date of Event or Censor
Tumor progression or death	Event	Earliest date of PD or death
No tumor progression and no death	Censored	Date of last adequate tumor assessment, per RECIST 1.1 criteria, or date of randomization (whichever is later) ^b
Unless		
No baseline radiologic tumor assessment available	Censored	Date of randomization

Situation	Event/Censor	Date of Event or Censor
No adequate postbaseline tumor assessment available and death reported after 2 scan intervals following randomization ^b	Censored	Date of randomization
Tumor progression or death documented immediately after 2 or more scan intervals following last adequate tumor assessment or randomization (whichever is later) ^{a,b}	Censored	Date of last adequate tumor assessment, per RECIST 1.1 criteria, or date of randomization (whichever is later) ^a

Abbreviations: CR = complete response; PD = progressive disease; PFS = progression-free survival; PR = partial response; RECIST 1.1 = Response Evaluation Criteria in Solid Tumors, Version 1.1; SD = stable disease.

- ^a Adequate tumor assessment per RECIST 1.1 criteria refers to an assessment with 1 of the following responses CR, PR, SD, or PD.
- ^b Following the schedule of activities in the protocol, scans should be performed approximately every 2 cycles through Cycle 5, then approximately every 3 cycles until objective disease progression, death, or study completion.

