3.2. Schedule of Activities

This section includes the following SoA:

- Screening, Treatment, and Post-Discontinuation Follow-Up SoA for all participants
- Continued-Access SoA for participants on abemaciclib (See Section 7.8.1 of the CAMPFIRE Master Protocol for additional details)

Overview

The windows for the SoA and administration of first dose are based on calendar days.

At any time in the study, laboratory and pregnancy tests may be collected at a local clinic in accordance with local laws and regulations if deemed appropriate by the investigator. All results should be reviewed and recorded in the eCRF. A virtual visit with the study investigator is not required for a local lab draw or pregnancy test.

Screening and Baseline

The screening period allows up to 28 days for confirmation of eligibility and completion of baseline assessments.

Treatment Period

Cycles are 21 days. During the on-study treatment period, participants will return to clinic on Days 1-5 for IV infusions. Additional evaluations on Day 8 and Day 15 of each cycle will be conducted on-site, remotely (that is, by telephone, IT-assisted virtual visit, mobile healthcare, or a combination thereof) or a combination of remote and on-site at the direction of the sponsor, according to local laws and regulations.

Treatment will continue until disease progression, unacceptable treatment-related toxicity, or participant or physician decision to discontinue.

Tumor Response

Tumor response per RECIST 1.1 should be assessed approximately every 2 cycles (at Cycles 3 and 5) and then every 3 cycles (beginning Cycle 8) until the participant has objective disease progression, death, or study completion.

Short- and Long-Term Follow-Up

Participants discontinuing study intervention will return for a short-term follow-up visit (Visit 801). The short-term follow-up visit will take place 30 days (± 14 days) after the decision is made to discontinue all study treatment.

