3.6.1.1. Exceptions to the CAMPFIRE Master Protocol Inclusion Criteria

For Study JP04, the below inclusion criteria should be used in place of the CAMPFIRE Master Protocol inclusion criteria of the corresponding number.

[1] Refractory disease or confirmed radiological progression or recurrence following first or later line of treatment of Ewing's sarcoma or Ewing's sarcoma-like tumor.

a. Must have one measurable or evaluable lesion per RECIST 1.1 (Eisenhauer et al. 2009)

[3] Adequate performance status based on age

a) For participants <16 years of age, a Lansky score ≥ 50 , or

b) For participants ≥ 16 years of age, a Karnofsky score ≥ 50

Note: Participants who are unable to walk because of paralysis, but are up in a wheelchair, will be considered ambulatory for the purpose of assessing the performance score

[4] Participants must have discontinued all previous treatments for cancer or investigational agents as shown below and must have recovered from the acute effects to Grade ≤ 1 at the time of

enrollment, unless otherwise noted (Grade ≤ 2 for alopecia, decreased tendon reflex, and residual peripheral sensory neuropathy are acceptable) or as specified in Inclusion Criterion 5. For agents with known AEs occurring beyond the required wait period outlined in the table, this period must be extended until after the time during which the AE is known to occur. For additional therapies not mentioned in the table, including targeted therapies, consult with the Lilly CRP/CRS for the appropriate length of time prior to the first dose of study treatment.

Previous Treatment	Length of Time Prior to First Dose of Study Treatment
Cytotoxic and myelosuppressive chemotherapy	≥ 21 days after myelosuppressive or cytotoxic chemotherapy ≥ 42 days if prior nitrosourea
Hematopoietic growth factors	≥ 14 days after long-acting growth factor (e.g., pegfilgrastim) ≥ 7 days for short-acting growth factor
Cellular therapy	≥ 42 days after cellular therapy (e.g., modified T or NK cells)
Interleukins, interferons, and cytokines	≥ 21 days after interleukins or interferon and cytokines (other than hematopoietic growth factors)
Radiotherapy	≥ 14 days after small port (i.e., local palliative) ≥ 84 days after large-field ($\geq 50\%$ of pelvis or TBI) ≥ 42 days for other substantial bone marrow radiation
Autologous stem cell infusion	≥ 84 days

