3.9.1. Efficacy Assessments

Tumor assessments will be performed for each participant at the times shown in the SoA (Section 3.2).

Computed tomography scans, including spiral CT, are the preferred methods of measurement (≤ 5 mm scan thickness recommended); however, MRI is also acceptable in certain situations, such as when body scans are indicated or if there is a concern about radiation exposure associated with CT. Contrast agent (intravenous or oral) is required unless medically contraindicated.

The CT portion of a PET-CT scan may be used for response assessment if the CT is of equal diagnostic quality to a diagnostic CT (with intravenous and oral contrast). A PET scan alone or as part of a PET-CT cannot be used for response assessment according to RECIST 1.1 (Eisenhauer et al. 2009).

The method of tumor assessment used at baseline must be used consistently throughout the study. Radiologic scan of the chest, abdomen, and pelvis is required.

For participant with evaluable disease only, response assessments should be made according to RECIST 1.1 for non-target disease only.

Scans will be performed and reviewed locally for treatment-based decisions. Because evaluation of tumor assessments for the primary objective will occur by a blinded independent review committee, scans will also be collected and stored centrally.

See Section 3.10.3.1 for definitions of the efficacy endpoints.

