7.7.2. Secondary Efficacy Analyses

Overall survival (OS) is defined as the time from randomization until death from any cause. If the patient is alive or lost to follow-up at the time of data analysis, OS data will be censored on the last date the patient is known to be alive. The following analyses will be conducted for OS:

- Kaplan-Meier curves (Kaplan and Meier 1958) will be generated; medians, quartiles, and appropriate point probabilities will be calculated. Interval estimates will be calculated. The OS rates at 1, 2, and 3 years for each treatment group will be estimated and compared using a normal approximation for the difference between the rates
- The Cox regression stratified by the randomization factors will be used to estimate the HR between the 2 treatment groups.

Objective response rate (ORR) is defined as the number of participants who achieve a best overall response of CR or PR divided by the total number of participants randomized to the corresponding treatment arm (ITT population). The ORR, with CCI CI, will be summarized for each treatment arm and compared between treatment arms using the Cochran-Mantel-Haenszel test adjusting for the randomization strata.

Duration of response (DoR) is defined as the time from the date that measurement criteria for CR or PR (whichever is first recorded) are first met until the first date that disease is recurrent or documented disease progression is observed, per RECIST 1.1 criteria, or the date of death from any cause in the absence of documented disease progression or recurrence. DoR will be calculated only for patients with confirmed PR or CR. DoR will be summarized for each treatment arm using descriptive statistics.

Disease control rate (DCR) is defined as the number of participants who achieve a best overall response of CR, PR, or SD, divided by the total number of participants randomized to the corresponding treatment arm (ITT population). DCR will be summarized for each treatment arm using descriptive statistics.

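### The closed list defining an adequate tumor assessment omits non-CR/non-PD, so read literally the stable scans of participants with evaluable-only disease count for neither PFS nor DCR

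*SAP*

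**What the plan says.** Four provisions meet here.

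- **Eligibility.** Protocol 3.6.1.1, replacement criterion [1]a: "Must have one measurable or evaluable lesion per RECIST 1.1". Measurable disease is therefore not required.
- **Response assessment.** Protocol 3.9.1: "For participant with evaluable disease only, response assessments should be made according to RECIST 1.1 for non-target disease only".
- **Censoring.** Footnote a, the same in SAP Table JP04.7.1 and protocol Table JP04.7: "Adequate tumor assessment per RECIST 1.1 criteria refers to an assessment with 1 of the following responses CR, PR, SD, or PD". The last row of each table censors a progression or death found immediately after "2 or more scan intervals following last adequate tumor assessment or randomization (whichever is later"). The censoring date is "Date of last adequate tumor assessment, per RECIST 1.1 criteria, or date of randomization (whichever is later"). The row for participants alive without progression uses the same date rule.
- **Disease control.** SAP 7.7.2: "Disease control rate (DCR) is defined as the number of participants who achieve a best overall response of CR, PR, or SD", over all participants randomized to the arm. Protocol 3.10.3.1.5 agrees.

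Neither document mentions non-CR/non-PD or says that a persisting non-target-only result is to be handled as SD.

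**The concern.** The protocol creates a group assessed only on non-target lesions, and the censoring table leaves out that group's ordinary stable result. If each scan before progression is non-CR/non-PD, none is adequate and the last adequate assessment stays at randomization. The table then treats these participants unevenly:

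- progression or death before two scan intervals have passed is an event;
- progression or death after that is censored at day 0;
- survival without progression, however long, is censored at day 0.

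The group thus contributes early failures and almost nothing else to the primary endpoint, PFS by blinded independent review. In DCR, a participant whose disease was held stable falls outside the numerator but stays in the denominator. In a trial that plans for at least 45 participants, a handful of lost events matters.

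**Working it through.** **What can be reproduced.** The planned event count, hazard ratio, alpha and power are redacted, so the sample size cannot be recomputed. The point does not depend on them.

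**Two scan intervals.** Protocol 3.2 gives "Cycles are 21 days" and scans "approximately every 2 cycles (at Cycles 3 and 5) and then every 3 cycles (beginning Cycle 8"). From Cycle 1 Day 1, taken as close to randomization:

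- scan days are (3 − 1) × 21 = 42, (5 − 1) × 21 = 84, (8 − 1) × 21 = 147, then every 63 days;
- two early intervals are 2 × 2 × 21 = 84 days, or 12 weeks.

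Progression first seen at day 147 or later is therefore censored at day 0 if all earlier scans were non-CR/non-PD. Progression at day 84 is on the boundary. The protocol refers the definition of two scan intervals to the SAP, and SAP footnote b restates the schedule without a day count or window. Both readings are shown below.

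**How many are still event-free at 84 days.** With exponential PFS and an assumed median of m months, P(T > 84 days) = 0.5^((84/30.4375)/m). This gives 53%, 62%, 73% and 81% for m = 3, 4, 6 and 9. The cut therefore falls before most events.

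**Size of the group.** The documents give no share. For 5%, 10%, 20% and 30% of 45, the numbers are 2.25, 4.5, 9 and 13.5 participants.

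**Events dropped at a fixed follow-up.** I simulated exponential PFS with 2:1 allocation, the scan grid above and 24 months of follow-up, and applied the table's rule to the evaluable-only share. The control median (4 or 6 months) and the true hazard ratio (0.6) are assumptions, not figures from the documents. Events are scaled to 45 participants. In each pair, the first figure counts day-84 progression as an event and the second censors it.

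| Evaluable-only share | Control median 4 months: events kept of about 42.1 | Dropped | Control median 6 months: events kept of about 38.1 | Dropped |
|---|---|---|---|---|
| 5% | 40.7 / 40.4 | 3.5% / 4.2% | 36.6 / 36.4 | 3.8% / 4.4% |
| 10% | 39.2 / 38.6 | 6.8% / 8.3% | 35.2 / 34.8 | 7.5% / 8.6% |
| 20% | 36.3 / 35.1 | 13.7% / 16.6% | 32.4 / 31.5 | 15.1% / 17.6% |
| 30% | 33.5 / 31.7 | 20.6% / 24.7% | 29.5 / 28.2 | 22.6% / 26.0% |

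The loss is close to the share times 0.7 to 0.9 (for example 13.7/20 = 0.69 and 17.6/20 = 0.88). It can be rescaled once the true share is known.

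**Concurrent hazard ratio.** The ratio of events per exposure between arms moved by about 0.01 or less in every scenario (for example from 0.632 to 0.622 at a 30% share and a 4-month median).

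**DCR.** The understatement is the evaluable-only share times the proportion of that group whose best result is stable. If two thirds are stable (assumed), 20% × 2/3 = 13 percentage points, and 5% to 30% gives 3 to 20 points.

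**The case against.** The strongest objection is that the key label is not in the documents. Non-CR/non-PD comes from RECIST 1.1, which both documents adopt but do not reproduce. The case report form and the independent review charter are not available here. If readers record a stable non-target-only scan as SD, the problem disappears for PFS and DCR alike. This stands as a condition on the conclusion. It does not remove the gap: the list is closed, the protocol prescribes non-target assessment for this group, and nothing written maps the result to SD. A participant with an earlier recorded CR is also unaffected.

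A second objection is that the primary analysis is triggered by an event count (protocol 3.10.3.1.1). If the trigger counts events after the censoring rules are applied, the cost is mainly time rather than events. With an assumed 36-event trigger and 18 months of accrual, the delay at a 10% share is about 2.5 to 5 months, and longer at higher shares. This stands too, so the table above describes a fixed follow-up.

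A reader might infer more than the documents support:

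- **A stated loss of power.** The event count, hazard ratio, alpha and borrowing model are redacted, so no power loss can be given for the planned Bayesian rule.
- **A biased treatment effect.** The average concurrent hazard ratio hardly changes. Bias from a chance imbalance in evaluable-only disease is conceivable but has not been quantified. A shift against the historical controls cannot be sized while the borrowing model is redacted.
- **A flawed ORR.** Keeping all randomized participants in the denominator is the prespecified ITT definition, not an error.

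**Conclusion.** The point holds on the text as written. Unless non-CR/non-PD scans are recorded as SD, participants with evaluable-only disease have no adequate stable assessment. Their progression or death from about 84 days on, and all their event-free time, are then censored at randomization, and their disease control is not counted.

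The size depends on a share that the documents do not give. Over assumed shares of 5% to 30%, about 4% to 26% of PFS events are dropped at a fixed follow-up, or the analysis is delayed. These figures rest on exponential PFS, assumed medians, an assumed hazard ratio and an 84-day limit inferred from the schedule. The firm harm is lost information on the primary endpoint and an understated DCR, not a demonstrated bias in the hazard ratio between the randomized arms.

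**What to change.** 1. In footnote a of SAP Table JP04.7.1 and protocol Table JP04.7, list CR, PR, SD, non-CR/non-PD, or PD. Alternatively, state that non-CR/non-PD is treated as SD.
2. In SAP 7.7.2 and protocol 3.10.3.1.5, count non-CR/non-PD as disease control in the DCR numerator.
3. Check that the independent review and investigator response fields carry the same category, so that both PFS analyses use one rule.

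The cost is two footnotes and the matching DCR lines. No new data or assessments are needed. The change should be made before treatment codes are unblinded for the primary analysis. If scans are already coded as SD, it only writes down existing practice.
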